8.1.2 DEFINITION OF SERIOUS ADVERSE EVENTS (SAE)

An AE or suspected adverse reaction is considered "serious" if, in the view of either the Investigator or Sponsor, it results in any of the following outcomes:

- * Death
- * A life-threatening adverse event
- * Inpatient hospitalization or prolongation of existing hospitalization
- * A persistent or significant incapacity or substantial disruption of the ability to conduct normal life functions
- * A congenital anomaly/birth defect

Important medical events that may not result in death, be life-threatening, or require hospitalization may be considered serious when, based upon appropriate medical judgment, they may jeopardize the patient or subject and may require medical or surgical intervention to prevent one of the outcomes listed in this definition.

8.1.3 DEFINITION OF UNANTICIPATED ADVERSE DEVICE EFFECT (UADE)

Unanticipated adverse device effect is any serious adverse effect on health or safety, any life-threatening problem or death caused by, or associated with a device, if that effect, problem, or death was not previously identified in nature, severity, or degree of incidence in the application; or any other unanticipated serious problem associated with a device that relates to the rights, safety, or welfare of subjects.

8.2 CLASSIFICATION OF AN ADVERSE EVENT

8.2.1 SEVERITY OF EVENT

The Investigator will be asked to assess the severity of the AE using the following categories:

- Mild:** Events require minimal or no treatment and do not interfere with the participant's daily activities.
- Moderate:** Events result in a low level of inconvenience or concern with the therapeutic measures. Moderate events may cause some interference with functioning.
- Severe:** Events interrupt a participant's usual daily activity and may require systemic drug therapy or other treatment. Severe events are usually potentially life-threatening or incapacitating.

8.2.2 RELATIONSHIP TO STUDY DEVICE

For all collected AEs, the clinician who examines and evaluates the participant will determine the AE's causality based on temporal relationship and his/her clinical judgment. The degree of certainty about causality will be graded using the categories below.

- Definitely:** The relationship of the AE and the study device or the study procedure can definitely be established.
- Probably:** While a clear relationship to the study device or to the study procedure cannot be established, the AE is associated with an expected AE or there is no other medical condition or intervention, which could explain the occurrence of such an event.
- Possibly:** There is no clear relationship between the AE and the study device or study procedure; however, one cannot definitely conclude that there is no relationship.
- Unrelated:** There is no relationship between the AE and the study device or study procedure. This may include but is not limited to the incident being an expected outcome of a previously existing or concurrent disease, concomitant medication or procedure the subject experienced.

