6.2 POTENTIAL RISKS AND BENEFITS

6.2.1 POTENTIAL RISK AND PRODUCT WARNINGS

MicroMatrix® and Cytal® Wound Matrix 2-Layer

Complications and reactions are possible with any soft tissue repair, including but not limited to:

- * infection
- * increased chronic inflammation
- * allergic reaction
- * unexplained fever or chills
- * excessive redness
- * pain
- * swelling

- * odor associated with the use of products during the healing phase
- * excessive drainage from the wound

Negative Pressure Wound Therapy

NPWT is contraindicated on the following situations:

- * exposed organs, blood vessels, vascular grafts, or unexplored enteric fistulas
- * active, untreated infection
- * necrotic tissue
- * malignancy tissue (within the wound)
- * fragile skin
- * active hemorrhage / coagulopathy / anticoagulation
- * adhesive allergy

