8.2.3 EXPECTEDNESS

The Investigator will be responsible for determining whether an AE is expected or unexpected. An AE will be considered unexpected if the nature, severity, or frequency of the event is not consistent with the risk information previously described for the study products.

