9. STATISTICAL CONSIDERATIONS

9.1 STATISTICAL AND ANALYTICAL PLANS

Primary Endpoint:

Wound area will be analyzed for size and percentage closure during specified subject follow up period. The mean, median and standard deviations will be calculated and scatter plots developed to determine healing rates by application number, and days in treatment. The mean number of application of product will be tabulated.

Safety will be assessed during the course of the study by collection of AEs as outlined in the Schedule of Events. All summaries of AEs will be based on treatment-emergent AEs and presented using the incidence and a tabulation of the number of events. The number and percentage of subjects experiencing AEs will be summarized by system organ class and description. Summaries by maximum severity and relationship to the study treatment will also be provided. SAEs and AEs leading to discontinuation from the study will be presented by system organ class and preferred term.

Baseline demographic factors patient characteristics and concomitant medications will be summarized. This summary will include the gender, age in years at the time of entry into the study, race, ethnicity, height (inches), weight (pounds) and BMI. Age, height, weight, and BMI will be summarized using descriptive statistics. The number and percent of each gender, race, and ethnicity category will be presented using counts and percentages.

The medical and surgical history will be coded for each patient and summarized based on the body system description. The patients will be summarized using counts and percentages for those patients who had a pre-study medical history.

Patient reported outcomes as measured using the Visual Analog Scale (VAS) and Katz Index of Independence in Activities of Daily Living (Katz ADL) will be summarized.

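### The causality grades in 8.2.2 pool the study device with an undefined study procedure and let expectedness alone support Probably, so the 9.1 relationship table cannot separate matrix-related events from procedure-related or ordinary postoperative ones.

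*Combined protocol and SAP*

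**What the plan says.** Section 8.2.2 defines four causality grades under a heading that names only the study device. The clinician is to grade from timing and clinical judgment.

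- *Definitely*: "The relationship of the AE and the study device or the study procedure can definitely be established".
- *Probably*: no clear relationship to device or procedure can be established, but "the AE is associated with an expected AE or there is no other medical condition or intervention" that could explain the event.
- *Possibly*: no clear relationship, but "one cannot definitely conclude that there is no relationship".
- *Unrelated*: no relationship to device or procedure, which may include "the incident being an expected outcome of a previously existing or concurrent disease, concomitant medication or procedure the subject experienced".

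Section 8.2.3 calls an event unexpected if it is "not consistent with the risk information previously described for the study products". That risk information is in 6.2.1, where the list for the two matrices opens with "Complications and reactions are possible with any soft tissue repair, including but not limited to" and then names infection, pain, swelling, excessive redness, odor and excessive drainage, among others.

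Section 8.3 lists one relationship item for collection, and it names the study device. Section 9.1 promises: "Summaries by maximum severity and relationship to the study treatment will also be provided".

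**The concern.** Three terms are used for what should be one attribution target: study device (heading of 8.2.2, and 8.3), device or procedure (the grades themselves) and study treatment (9.1). The protocol never says whether the study procedure is the excision, the application of the matrices, or both.

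The device term is not firm either. Section 6.1.1 describes the NPWT system under the study device heading, while the Protocol Summary lists only the two matrices as study products.

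The events affected are common ones. Section 8.1.1 sends all signs and symptoms related to the pilonidal disease and wound to the adverse event form from the index procedure onward, so ordinary postoperative complaints will be graded on this scale. In an uncontrolled series, the clinician's attribution is the only planned device attribution that covers all recorded adverse events. If it does not distinguish the matrices from the surgery, a reader of the 9.1 table may take surgical morbidity for a product effect, or miss a product effect recorded as surgical.

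**Working it through.** No figure in the plan needs reproducing, and the documents give no event rate. The check is a reading of the sections against one another, followed by a simple bound.

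**Inputs**
- Excision in every subject: inclusion criterion 2 (5.1).
- Matrices applied, and surgical details recorded, at the same visit: 7.1.3, items 3 and 6.
- NPWT for all wounds: section 3.
- At most 10 subjects in a single group: 4.1.
- Grades, expectedness rule and risk list: 8.2.2, 8.2.3 and 6.2.1.

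**Step 1. What expectedness does in *Probably*.** The two conditions are joined by *or*: (i) the event is associated with an expected one, or (ii) nothing else explains it. Condition (i) is enough by itself, so an evident alternative cause, which defeats (ii), does not exclude the grade. Wound pain, swelling, infection and excessive drainage all satisfy (i), because they are in 6.2.1.

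**Step 2. Trace wound pain after excision, which the clinician attributes to the surgery.**

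| Meaning of *study procedure* | Grades the wording supports | Tabulated as |
|---|---|---|
| Includes the excision | *Definitely* if the link to surgery is clear; otherwise *Probably* or *Possibly*. *Unrelated* is closed, because a relationship to the procedure exists | Related |
| Application of the matrices only | *Unrelated*, as an expected outcome of a "concomitant medication or procedure the subject experienced" | Not related |
| Application of the matrices only | *Probably*, because no clear relationship to the device can be established and pain is a listed event | Related |
| Application of the matrices only | *Possibly*, if a contribution from the matrices cannot be ruled out | Related |

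Under the broad meaning, a purely surgical event enters a device table as related. Under the narrow meaning, the clinician's conclusion that surgery was the cause still fits both *Unrelated* and the literal text of *Probably*; *Possibly* applies to a less certain clinician.

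**Step 3. Size.** Let k be the number of subjects, out of 10, with at least one event of this kind and no other event bearing on the count. Section 9.1 does not say which grades count as related; I take *Definitely*, *Probably* and *Possibly*.
- Lower end: narrow meaning, all graded *Unrelated*: 0/10.
- Upper end: broad meaning, or narrow meaning with condition (i) applied: k/10.

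k is an assumption and can be anything from 0 to 10. For k = 3 the range is 0/10 to 3/10 (0% to 30%); for k = 6 it is 0/10 to 6/10 (0% to 60%).

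**The case against.** A reader might go further and infer four things, none of which the documents support.

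1. *One event can be both Definitely and Unrelated.* It cannot. *Unrelated* opens by requiring that there be no relationship to device or procedure, and the clause about an expected outcome of a procedure only illustrates that condition. If the excision is the study procedure, an event it caused fails the condition; if it is not, it cannot support *Definitely*. The two ends of the scale need incompatible meanings of the term. *Definitely* and *Probably* also exclude each other, since *Probably* presupposes that no clear relationship can be established.
2. *Every expected event must be graded Probably.* The wording allows it, but the clinician first weighs timing and judgment.
3. *The related count swings from 0 of 10 to 10 of 10.* That is an outer bound. It needs every subject to have such an event and all assessors to take the same extreme reading.
4. *The study cannot show device toxicity at all.* Unanticipated adverse device effects are recorded and reported separately (8.1.3, 8.3, 8.4.3), expectedness is judged separately (8.2.3), and event onset and reapplications are recorded (8.3, 7.1.4), so timing can be examined.

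The best remaining argument is that three interventions act on one wound, so separate grades are still opinions and do not remove the confounding. That is true. But the present scale does not even record the opinion separately. The unanticipated-effect route covers only serious, unanticipated effects and leaves the 9.1 table as it is. Clinical judgment does not tell the assessor which meaning of the procedure applies, or which clause prevails.

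**Conclusion.** The point holds as a defect of definition with a limited but real effect. The grades pool device and procedure, the procedure is undefined, and expectedness alone can support *Probably*. As a result, the 9.1 summary cannot distinguish matrix-related events from procedure-related or ordinary postoperative ones. The number of subjects tabulated as related can vary from 0 to k of 10 through wording alone, with k not given.

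This rests on three assumptions: that the top three grades count as related; that the adverse event form, which is not in the documents, carries the single item named in 8.3; and that ordinary postoperative wound symptoms are recorded as 8.1.1 requires. It does not show that any event will be misgraded, nor that the study has no device-specific safety information. The change should be made before data collection, because attribution is hard to recover later if it was not recorded separately.

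**What to change.** 1. **8.2.2 and 8.3.** Grade causality on three separate lines: the matrices (MicroMatrix and Cytal), NPWT and the excision. Delete the procedure alternative from all four device grades. If that phrase was meant to cover application of the matrices, say so in the matrix line.
2. **8.2.2, *Probably*.** Remove the expected-event condition together with the *or* that follows it, leaving only the condition that nothing else explains the event. Expectedness is already determined under 8.2.3. Do not replace *or* with *and*: an unlisted event with no other cause, the kind most suggestive of a new product effect, could then not be graded *Probably*.
3. **9.1.** Tabulate by relationship to the matrices, with the NPWT and excision attributions beside it. State which grades count as related, and use the same term in 8.2.2, 8.3 and 9.1.

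The cost is a few lines of wording and, if the form has one relationship item, two more. Completion takes slightly longer. Because excision and NPWT are nearly always available as explanations, few listed events will reach *Probably* on the matrix line; most will be *Possibly* or *Unrelated*. Attribution among concurrent components remains a clinical judgment.

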8.2.3 EXPECTEDNESS

The Investigator will be responsible for determining whether an AE is expected or unexpected. An AE will be considered unexpected if the nature, severity, or frequency of the event is not consistent with the risk information previously described for the study products.

8.3 TIME PERIOD AND FREQUENCY FOR EVENT ASSESSMENT AND FOLLOW-UP

The occurrence of an AE or SAE may come to the attention of study personnel during study visits or upon review by a study monitor. All AEs (per Investigator discretion) that are

possibly impactful to the development or healing of a pilonidal wound will be captured on the appropriate data collection form. Information to be collected includes event description, time of onset, clinician's assessment of severity, relationship to study device (assessed only by those with the training and authority to make a diagnosis), and time of resolution/stabilization of the event. All AEs will be followed to adequate resolution.

Any medical condition that is present at the time that the participant is screened will be considered as baseline and not reported as an AE. However, if the study participant's condition deteriorates at any time during the study, it will be recorded as an AE. UADEs will be recorded throughout the study.

Changes in the severity of an AE will be documented to allow an assessment of the duration of the event at each level of severity to be performed. AEs characterized as intermittent require documentation of onset and duration of each episode.

8.4 REPORTING PROCEDURES

8.4.1 ADVERSE EVENT REPORTING

Adverse events will be documented on the appropriate data collection form as the Investigator learns of the event. The Investigator will follow all AEs until adequate resolution is achieved. If the event has not resolved by the end of the study, the status of the event should be documented as of study closure. The IRB should be notified of all AEs according to their notification policies.

8.4.2 SERIOUS ADVERSE EVENT REPORTING

In the case of a SAE, the Investigator must immediately notify (within 1 working day) the Sponsor (contact information is provided in **Section 1, Key Roles**). The IRB must also be notified according to their notification policies.

8.4.3 UADE REPORTING

The Investigator must immediately notify the study Sponsor and the reviewing IRB as soon as possible, but in no event later than 10 working days after the Investigator first learns of the effect. The study Sponsor is responsible for conducting an evaluation of an UADE and shall report the results of such evaluation to the reviewing IRB and the Investigator within 10 working days after the Sponsor first receives notice of the effect.

8.4.4 REPORTING OF PREGNANCY

If a female patient becomes pregnant during the trial, she must be followed up until the outcome of the pregnancy is known.

9. STATISTICAL CONSIDERATIONS

9.1 STATISTICAL AND ANALYTICAL PLANS

Primary Endpoint:

Wound area will be analyzed for size and percentage closure during specified subject follow up period. The mean, median and standard deviations will be calculated and scatter plots developed to determine healing rates by application number, and days in treatment. The mean number of application of product will be tabulated.

Safety will be assessed during the course of the study by collection of AEs as outlined in the Schedule of Events. All summaries of AEs will be based on treatment-emergent AEs and presented using the incidence and a tabulation of the number of events. The number and percentage of subjects experiencing AEs will be summarized by system organ class and description. Summaries by maximum severity and relationship to the study treatment will also be provided. SAEs and AEs leading to discontinuation from the study will be presented by system organ class and preferred term.

Baseline demographic factors patient characteristics and concomitant medications will be summarized. This summary will include the gender, age in years at the time of entry into the study, race, ethnicity, height (inches), weight (pounds) and BMI. Age, height, weight, and BMI will be summarized using descriptive statistics. The number and percent of each gender, race, and ethnicity category will be presented using counts and percentages.

The medical and surgical history will be coded for each patient and summarized based on the body system description. The patients will be summarized using counts and percentages for those patients who had a pre-study medical history.

Patient reported outcomes as measured using the Visual Analog Scale (VAS) and Katz Index of Independence in Activities of Daily Living (Katz ADL) will be summarized.

10 SOURCE DOCUMENTS AND CASE REPORT FORMS

Data collection is the responsibility of the clinical trial staff at the site under the supervision of the site Principal Investigator. The Investigator is responsible for ensuring the accuracy, completeness, legibility, and timeliness of the data reported. Study data will be collected on data collection forms and in the subject medical records.

All source documents should be completed in a neat, legible manner to ensure accurate interpretation of data. When making changes or corrections, cross out the original entry with a single line, and initial and date the change. **DO NOT ERASE, OVERWRITE, OR USE CORRECTION FLUID OR TAPE ON ANY ORIGINAL DOCUMENTS.**

Study personnel at each site will enter data from source documents corresponding to a subject's visit into the protocol-specific CRF when the information corresponding to that visit is available. Subjects will not be identified by name on any study documents to be collected by the Sponsor (or designee), but will be identified by a subject number and initials.

The handling of the data by the Sponsor after receipt of the CRFs may generate additional requests to which the Investigator is obliged to respond by confirming or modifying the data questioned.

11 ETHICS/PROTECTION OF HUMAN SUBJECTS

11.1 ETHICAL STANDARD

The Investigator will ensure that this study is conducted in full conformity with Regulations for the Protection of Human Subjects of Research codified in 45 CFR Part 46, 21 CFR Part 50, 21 CFR Part 56, and/or the ICH E6.

11.2 LAWS AND REGULATIONS

This clinical study will be conducted in compliance with all national laws and regulations of the countries in which the clinical trial is performed, as well as any applicable guidelines. The trial will be registered on www.clintrials.gov and on other sites, as appropriate.

11.3 INSTITUTIONAL REVIEW BOARD

The protocol, informed consent form(s) and all participant materials will be submitted to the IRB for review and approval. Approval of both the protocol and the consent form must be obtained before any participant is enrolled. Any amendment to the protocol will require review and approval by the IRB/IEC before the changes are implemented to the study. All changes to the consent form will be IRB approved; a determination will be made regarding whether previously consented participants need to be re-consented.

11.4 INFORMED CONSENT PROCESS

Informed consent is a process that is initiated prior to the individual's agreeing to participate in the study and continues throughout the individual's study participation. Extensive discussion of risks and possible benefits of participation will be provided to the participants and their families. Consent forms will be IRB approved and the participant will be asked to read and review the document. The Investigator will explain the research study to the participant and answer any questions that may arise. All participants will receive a verbal explanation in terms suited to their comprehension of the purposes, procedures, and potential risks of the study and of their rights as research participants. Participants will have the opportunity to carefully review the written consent form and ask questions prior to signing. The participants should have the opportunity to discuss the study with their surrogates or think about it prior to agreeing to participate. The participant will sign the informed consent document prior to any procedures being done specifically for the study. The participants may withdraw consent at any time throughout the course of the trial. A copy of the informed consent document will be given to the participants for their records. The rights and welfare of the participants will be protected by emphasizing to them that the quality of their medical care will not be adversely affected if they decline to participate in this study.

If a consent document is revised due to changes in study procedures, subjects who were enrolled prior to the change, but are affected by the change, will be informed of the changes and will sign the amended consent document. If a consent document is revised due to changes in the risks or safety of the study, all active participants must sign the revised consent.

